#### **8.4.7 Health Care Resource Utilization**

For this study the following health care resource utilization (HCRU) parameters collected during the study observation period will be summarized for the Safety population:

- Type of admission (hospital, intensive care unit (ICU), emergency unit)
- Descriptive statistics of number of hospital visits per subject
- Descriptive statistics of number of ICU visits per subject
- Descriptive statistics of number of emergency room (ER) visits per subject
- Total person-years of observation
- Total days of hospitalization
- Days of hospitalization per person-year
- Total days of ICU visit
- Days of ICU visit per person-year

Person-years total is calculated as the sum of [(end date of safety observation period – first dose date +1)/365.25] across all subjects in the given treatment group. For placebo crossover subjects, total person-year is calculated as the sum of [(end date of safety observation period – first dose date of open-label cabozantinib +1)/365.25] across all subjects who have crossed over. To calculate the per person year value for a subject for a HCRU parameter, the numerator is the sum of the days or visits for that subject for the parameter; and the denominator is the applicable person-years of observation as defined.

#### **8.4.8 Pharmacokinetics (PK)**

Pharmacokinetics analyses are outside the scope of this plan. A separate PK analysis plan and report will be provided.

## 8.5 Subgroups

The following subgroups based on baseline characteristics and stratification factors will be explored for the primary efficacy endpoints and Overall Survival. Summary tables will be provided for the OITT and ITT populations. Forest plots will be provided for hazard ratios/odds ratio as applicable.

- Receipt of prior lenvatinib per CRF
  - Yes
  - No
- Receipt of prior sorafenib per CRF
  - Yes
  - No
- Receipt of prior sorafenib and lenvatinib per CRF
  - Yes
  - No
- Age category per CRF
  - $\leq 65$  years
  - $> 65$  years
- Sex
  - Male
  - Female
- Race
  - Asian
  - Black or African American
  - White
  - Rest of the races reported/Not Reported
- Regions
  - Asia
  - USA/Canada/Europe
  - Rest of the world
- ECOG Performance status at baseline:
  - 0
  - 1

- Prior VEGFR-TKI anticancer therapy agents for DTC per subject per history of non-radiation anticancer therapy CRF (0, 1,  $\geq 2$ )
- Prior receipt of RAI (Yes, No)
- Histology
  - Papillary
  - Follicular
- Bone Metastasis per Investigator
  - No
  - Yes
- Important Visceral Metastasis per Investigator
  - No
  - Yes
- Liver Metastasis per Investigator
  - No
  - Yes
- Lung Metastasis per Investigator
  - No
  - Yes

## **9 SAFETY SUMMARIES**

All safety analyses will be performed on data as described in Section 4.6 for subjects in the Safety population. No formal statistical comparison between the two treatments arms is planned.

Safety and tolerability will be assessed by the incidence of treatment emergent-adverse events (TEAEs), changes in laboratory parameters and vital signs from baseline, and ECOG PS.

An Independent Data Monitoring Committee (IDMC) will monitor safety of the subjects during the study on a regular basis. The committee will operate independently from the Sponsor and the clinical investigators.

The primary responsibility of the IDMC is to review the accumulating safety data on a regular and an ad hoc basis and make recommendations to the Sponsor regarding the

continued conduct of the study. Safety data will be provided at regular intervals to the IDMC in the form of summary reports or data listings from the Sponsor (blinded) or its designated representative (unblinded).

Details regarding IDMC membership, schedule and format of meetings, format for presentation of data, access to interim data, method and timing of providing interim reports to the IDMC, and other issues relevant to committee operations are described in the IDMC charter.

The IDMC members will use their expertise, experience, and judgment to evaluate the safety data from the trial and to recommend to the Sponsor whether the trial should continue or be stopped early for safety. No formal statistical rules recommending early stopping for safety are planned.

## **9.1 Adverse Events**

Adverse event terms recorded on the CRF will be mapped to preferred terms and system organ class using the Medical Dictionary for Regulatory Activities (MedDRA). The severity of AEs will be measured by CTCAE version 5 guidelines. The investigator will judge each event to be “not related” or “related” to study treatment.

A TEAE is defined as any event with an onset date on or after the date of the first dose of study drug or any ongoing event on the date of the first dose of study drug that worsens in severity after the date of the first dose of study drug.

Only TEAEs with an onset date through the end of the safety observation period (see Section 4.6) will be tabulated in summary tables.

For the purpose of calculating treatment emergence and inclusion in summary tables, incomplete onset dates will be imputed as detailed in Appendix A.

For AE reporting, percentages  $\geq 10\%$  will generally be presented as integers, those  $< 10\%$  will be presented with 1 decimal place (e.g. X.X%). Rounding rules are provided in Appendix B. The calculations of percentages will be based on original unrounded values.

An overall summary of adverse events will be provided with the number and percent of subjects who experienced the following types of events during the safety observation period (unless otherwise noted as “at any time” below) in each treatment arm:

- Subjects with a TEAE
- Subjects with a Related TEAE
- Subjects with a Serious TEAE
- Subjects with a Serious Related TEAE at any time
- Subjects with a Worst-Grade 3 or 4 TEAE
- Subjects with a Worst-Grade 3 or 4 Related TEAE
- Subjects with a Worst-Grade 4 TEAE
- Subjects with a Worst-Grade 4 Related TEAE
- Subjects with a Grade 5 TEAE (death)  $\leq$  30 days after the last dose of the study treatment
- Subjects with a Grade 5 TEAE (death) judged not to be causally related to disease under study  $\leq$  30 days of last dose of the study treatment
- Subjects with a Related Grade 5 TEAE at any time (all treatment-related deaths)
- Subjects with a Related Grade 5 TEAE (death)  $\leq$  30 days after the last dose of the study treatment
- Subjects with a TEAE leading to Dose Modification
- Subjects with a TEAE leading to Dose Reduction
- Subjects with a TEAE leading to Dose Hold
- Subjects with TEAE leading to Treatment Discontinuation
  - TEAEs not causally related to disease under study
    - TEAEs related to study treatment
    - TEAEs not related to study treatment
  - TEAEs causally related to disease under study
    - TEAEs related to study treatment

The following summaries of AEs will be provided:

| TEAE included  | Row-levels (sorted by)   | Columns will Display                                |
|---|---------------------------------|--|
| Subject Incidence by SOC, Preferred Term and Severity |                                 |  |
| All   | SOC and PT
(MedDRA standard) | Worst severity:
All Grades, Grade 3/4, Grade 4, Grade 5 |
| Related   | SOC and PT
(MedDRA standard) | Worst severity:
All Grades, Grade 3/4, Grade 4, Grade 5 |
| Serious   | SOC and PT
(MedDRA standard) | Worst severity:
All Grades, Grade 3/4, Grade 4, Grade 5 |
| Subject Incidence by Preferred Term and Severity      |                                 |  |

| TEAE included  | Row-levels (sorted by)   | Columns will Display   |
|---|---|---|
| All   | PT
(descending frequency of Any Grade)   | Worst severity:
All Grades, Grade 3/4, Grade 4, Grade 5                    |
| All   | PT
(descending frequency of Grade 3/4)   | Worst severity:
All Grades, Grade 3/4, Grade 4, Grade 5                    |
| All   | PT
(descending frequency of Any Grade)   | Worst severity:
All Grades, Grade 1, Grade 2, Grade 3,
Grade 4, Grade 5 |
| Related   | PT
(descending frequency of Any Grade)   | Worst severity:
All Grades, Grade 3/4, Grade 4, Grade 5                    |
| Related   | PT
(descending frequency of Grade 3/4)   | Worst severity:
All Grades, Grade 3/4, Grade 4, Grade 5                    |
| Serious   | PT
(descending frequency of Any Grade)   | Worst severity:
All Grades, Grade 3/4, Grade 4, Grade 5                    |
| Related and Serious   | PT
(descending frequency of Any Grade)   | Worst severity:
All Grades, Grade 3/4, Grade 4, Grade 5                    |
| Leading to dose reduction   | PT
(descending frequency of Any Grade)   | Worst severity:
All Grades, Grade 3/4, Grade 4, Grade 5                    |
| Leading to dose reduction   | PT
(descending frequency of Grade 3/4)   | Worst severity:
All Grades, Grade 3/4, Grade 4, Grade 5                    |
| Leading to dose hold  | PT
(descending frequency of Any Grade)   | Worst severity:
All Grades, Grade 3/4, Grade 4, Grade 5                    |
| Leading to dose hold  | PT
(descending frequency of Grade 3/4)   | Worst severity:
All Grades, Grade 3/4, Grade 4, Grade 5                    |
| Leading to dose modification  | PT
(descending frequency of Any Grade)   | Worst severity:
All Grades, Grade 3/4, Grade 4, Grade 5                    |
| Leading to dose modification  | PT
(descending frequency of Grade 3/4)   | Worst severity:
All Grades, Grade 3/4, Grade 4, Grade 5                    |
| Not Causally Related to Disease Under Study Leading to Study Treatment Discontinuation  | PT
(descending frequency of Any Grade)   | Worst severity:
All Grades, Grade 3/4, Grade 4, Grade 5                    |
| Not Causally Related to Disease Under Study and Related to Study Treatment and Leading to Study Treatment Discontinuation     | PT
(descending frequency of Any Grade)   | Worst severity:
All Grades, Grade 3/4, Grade 4, Grade 5                    |
| Not Causally Related to Disease Under Study and Not Related to Study Treatment and Leading to Study Treatment Discontinuation | PT
(descending frequency of Any Grade)   | Worst severity:
All Grades, Grade 3/4, Grade 4, Grade 5                    |
| Causally Related to Disease Under Study and Leading to Study Treatment Discontinuation  | PT
(descending frequency of Any Grade)   | Worst severity:
All Grades, Grade 3/4, Grade 4, Grade 5                    |
| Causally Related to Disease Under Study and Related to Study Treatment and Leading to Study Treatment Discontinuation         | PT
(descending frequency of Any Grade)   | Worst severity:
All Grades, Grade 3/4, Grade 4, Grade 5                    |
| Subject Incidence of AEs with Odds ratio, Relative Risk and Risk Difference  |   |   |
| All   | PT
(descending frequency of difference)  | Worst severity:
All grades, Grades 3/4                                     |
| ≤ 30 days after the last dose of study treatment  | PT
(descending frequency of Grade 5)   | Worst severity:
Grade 5  |
| AEs judged not to be causally related to disease under study ≤ 30 days of last dose of study treatment                        | PT
(descending frequency of Grade 5)   | Worst severity:
Grade 5  |
| Related to study treatment at any time  | PT
(descending frequency of Grade 5)   | Worst severity:
Grade 5  |
| Related to study treatment and ≤ 30 days after the last dose of study treatment   | PT
(descending frequency of Grade 5)   | Worst severity:
Grade 5  |
| Subject Incidence by Special Criteria  |   |   |
| Events with an increase in the experimental arm of ≥5% (All Grades) or ≥2% (Grade 3/4)  | SOC and PT
(SOC per MedDRA standard, PT within SOC by decreasing difference in percent for All Grades) | Worst severity:
All Grades, Grade 3/4, Grade 4, Grade 5                    |
| Subject incidence of non-serious adverse event with frequency in  | SOC and PT
(SOC per MedDRA standard, PT within   | Worst severity:
All Grades, Grade 3/4, Grade 4, Grade 5                    |

| TEAE included                              | Row-levels (sorted by)   | Columns will Display                                |
|---|---|--|
| the experimental arm of $\geq 5\%$
(Any Grade) | SOC by decreasing frequency in percent for All Grades)                                    |  |
| All   | PT
(descending frequency of difference in percent between the two arms for All Grades) | Worst severity:
All Grades, Grade 3/4, Grade 4, Grade 5 |
| All   | PT
(descending frequency of difference in percent between the two arms for Grade 3/4)  | Worst severity:
All Grades, Grade 3/4, Grade 4, Grade 5 |

The following data listings will also be provided with indicators for grade, relationship, seriousness, dose day of the event start/stop, days since last dose, actions taken with study treatment:

- All AEs
- Grade 5 AEs (deaths)
- Serious AEs other than death
- All AEs that led to treatment discontinuation

All adverse events summaries will also be provided for the O-Safety population.

## 9.2 Events to Monitor

The sponsor has defined a set of events to monitor (ETM) to track adverse events known to be associated with TKIs or VEGF pathway inhibition that have potentially serious consequences, or were determined to warrant ongoing routine surveillance. Each ETM is a grouped clinical term comprising a broad set of AEs that are related pathophysiologically and provide a consistent, reproducible, and transparent compilation of safety information over time. These ETMs may also be identified in the current cabozantinib product labeling (MTC US package insert and EU SmPC) or in the EU RMP document as known or potential risks and precautions.

The following summaries will be provided for ETMs (Appendix F) for the Safety and O-Safety Populations:

**Table 12: Summaries for ETM**

| TEAE included   | Row-levels (sorted by)  | Columns  |
|---|---|--|
| Subject Incidence by SOC, Preferred Term and Severity |   |  |
| All ETM AEs   | ETM and PT (ETM , PT within ETM by descending frequency)            | Worst severity:
All Grades, Grade 3-4, Grade 4, Grade 5 |
| All ETMs of Grade >=3   | ETM and PT (ETM, PT within ETM by descending frequency)             | Worst severity:
Grade >=3, Grade 3, Grade 4, Grade 5    |
| Subject Incidence by Special Criteria                 |   |  |
| All ETM AEs by age (<=65 years, >65 years), ECOG, region, race, sex | ETM and PT (ETM , PT within ETM by descending frequency)            | Worst severity:
Any Grades, Grade 3-4, Grade 4, Grade 5 |
| Time to First Occurrence                              |   |  |
| All ETM AEs and Grade >=3   | Time to first occurrence of Adverse Events to Monitor by Group Term |  |

## 9.3 Treatment-emergent Adverse Events Adjusted by Treatment Duration

Summaries will be provided for all TEAEs, TEAEs with Grade 3 and above, and serious TEAEs adjusted for treatment exposure for the safety population. The AE rate (episode/subject-year) will be calculated as (Total occurrence for an AE episode/Total Subject-years for the respective treatment group). Total subject years for the respective treatment group is calculated as the sum of treatment exposure time in (years) for all subjects in the given treatment group. Treatment exposure in years is calculated as (treatment exposure in days as defined in Section 6.5/365.25). A single episode of an AE is defined from onset through resolution, or, if ongoing, to the end of the reporting period.

## 9.4 Deaths

All subject deaths (Grade 5 TEAEs) will be summarized for all subjects in the Safety and O-Safety populations.

Deaths will be summarized in two main categories as follows:

- Deaths after receipt first dose of study treatment and  $\leq 30$  days after the date of receipt of the last dose of study treatment
- Deaths  $> 30$  days after the date of receipt of last dose of study treatment

In addition, under each category causality to study disease will also be summarized.

All reported subject deaths will be listed.

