### **5.4.2 Extended Follow-up**

Following treatment discontinuation for whatever reason, subjects will continue to be followed either via clinic visit or telephone contact approximately every 12 weeks ( $\pm$  7 days) for the following information unless the subject withdraws consent for non-interventional study assessments:

- Survival status of the subject or date of death and primary cause of death
- Receipt of NPACTs: drug or procedure name and start/stop dates
- Information on subsequent progression following systemic NPACT (eg, date of subsequent radiographic progression or last known radiographic assessment)

Radiographic disease assessments and EQ-5D-5L are to continue in the Extended Follow-Up period as necessary per the schedule for these assessments in Appendix A, unless the subject withdraws from study interventions.

Subjects will be followed until death or until the Sponsor's decision to no longer collect these data.

At each contact, the investigator (or designee) will determine if the subject died, and if so, record the date and cause of death. All efforts must be undertaken by the study sites to determine the date of death (or date subject last known alive at the time of a data cut-off). This may include, but not necessarily be limited to, telephone contacts, communication at study visits, registered letters, and reviews of local obituaries and government death records (where allowed by local regulations). If subject is lost to follow-up, multiple attempts to contact must be made and documented in the subject records.

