### **9.6.1 Adverse Events**

Adverse event terms recorded on the CRFs will be mapped to preferred terms using the Medical Dictionary for Regulatory Activities (MedDRA) dictionary. The investigator will classify the severity of AEs using the CTCAE v5 and will judge each event to be “not related” or “related” to study treatment.

A treatment emergent adverse event (TEAE) is defined as any event that begins or worsens on or after date of first dose of study treatment.

The frequency and percentage of subjects with TEAEs will be tabulated for overall incidence by system organ class and preferred term by treatment arm. Related TEAEs, serious TEAEs, related serious TEAEs, TEAEs resulting in study treatment discontinuation and TEAEs resulting in study treatment modification (either dose reduction or dose delay) will be similarly summarized. TEAEs and related TEAEs will also be summarized for worst reported severity within each subject.

At each level of summarization, a subject will be counted only once for each AE preferred term he/she experiences within that level (ie, multiple episodes of events with the same preferred terms will be counted only once).

All reported subject deaths will be summarized by treatment arm, cause of death, and relationship to study treatment.

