#### **4.6 Safety Observation Period**

The safety observation period is defined as follows for the summaries described above in Section 4.1:

The safety observation period for subjects randomized to and receiving any cabozantinib is defined as the time between the date of first dose of cabozantinib to the earlier of the date of last dose of cabozantinib +30 days, or date of withdrawal of consent by subject, or date of death, or date of data cut-off.

The safety observation period for all subjects receiving placebo only during the blinded treatment period is defined as the time between the date of first dose of placebo to the earlier of the date of last dose of placebo, or date of withdrawal of consent by subject, date of death, or date of receipt of open-label cabozantinib -1, or date of data cut-off.

Subjects crossing over from placebo to cabozantinib will have data from the crossover period summarized independently. The post-crossover safety observation period of all subjects receiving cabozantinib after crossing over from placebo is defined as the time between the date of first dose of open-label cabozantinib to the earlier of the date of last dose of open-label study treatment +30 days, or date of withdrawal of consent by subject, or date of death, or date of data cut-off.

Generally only the safety data (including adverse events, laboratory results, vital signs, ECG, ECOG PS, concomitant medications and etc.) reported during the safety observation period will be analyzed and summarized, unless otherwise specified in this plan.

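### Read literally, SAP 9.4 limits its death table to Grade 5 TEAEs, which conflicts with its own row for deaths after 30 days, treats the arms unequally within 30 days, and departs from Protocol 9.6.1

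*Combined protocol and SAP*

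**What the plan says.** SAP 9.4 (Deaths) opens: "All subject deaths (Grade 5 TEAEs) will be summarized for all subjects in the Safety and O-Safety populations". It sets two timing categories, the second being deaths more than 30 "days after the date of receipt of last dose of study treatment". Under each it asks for causality to the study disease, and it ends by promising a listing of all reported deaths.

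SAP 9.1 (Adverse Events) gives the definition: "A TEAE is defined as any event with an onset date on or after the date of the first dose of study drug", or an ongoing event that worsens after that date. It then limits what is shown: "Only TEAEs with an onset date through the end of the safety observation period (see Section 4.6) will be tabulated in summary tables".

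SAP 4.6 (Safety Observation Period) ends the cabozantinib period at "the earlier of the date of last dose of cabozantinib +30 days", or sooner at consent withdrawal, death or data cutoff. The placebo period ends at last dose, with no 30-day extension, or sooner for the same reasons or on the day before open-label cabozantinib. Table 4 in SAP 4.1 repeats both rules. SAP 4.6 generally confines safety summaries to this period, unless the plan specifies otherwise.

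Protocol 9.6.1 sets a wider scope: "All reported subject deaths will be summarized by treatment arm, cause of death, and relationship to study treatment". Protocol 5.4.2 lists what the 12-weekly contacts collect after treatment, including "Survival status of the subject or date of death and primary cause of death".

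**The concern.** The table is labelled with one set of events and asked to report another. A death from disease four months after stopping treatment belongs in the later row by its date. It is not a tabulated Grade 5 TEAE, because no adverse event began inside the window. A programmer who follows the label and one who follows the row will produce different tables.

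This table shows cause of death and timing relative to last dose by treatment group. The OS analysis shows neither. OS is descriptive in this trial, with no formal inference (Protocol 9.3, SAP 8.4.1.2), and an administrative look at OS for survival detriment is planned if the ORR null is rejected. A coherent death table is therefore worth having.

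**Working it through.** The plan states no number of deaths by timing, so there is no figure to reproduce. The check is to follow the rules through.

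**Step 1: which deaths pass the tabulation rule.** A death is tabulated as a Grade 5 TEAE only if the fatal event's onset is on or before the end of the observation period. Day 0 is the last dose. Assume the event began after first dose and that consent withdrawal, cutoff or crossover did not end the period early.

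| Onset of fatal event | Death | Cabozantinib (window to day 30) | Placebo (window to day 0) |
|---|---|---|---|
| By day 0 | By day 30 | Counted | Counted |
| Days 1–30 | By day 30 | Counted | Not counted |
| By day 0 | After day 30 | Counted | Counted |
| Days 1–30 | After day 30 | Counted | Not counted |
| After day 30 | After day 30 | Not counted | Not counted |

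The later row is not empty, because the limit applies to onset rather than to date of death. It holds only events that began inside the window. Lines 2 and 4 show the difference between arms. It removes placebo deaths, so in this table it works against cabozantinib.

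**Step 2: what is collected.** Protocol 8.1 records adverse events through 30 days after the decision to discontinue, in both arms alike. Protocol 8.2.1 adds later SAEs only if they are related to study treatment or study procedures, on the SAE form. Other later deaths arrive through survival follow-up as a date and primary cause, not as graded events. Placebo events on days 1–30 are therefore generally collected but would not be tabulated.

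**Step 3: comparison with the protocol.** Protocol 9.6.1 covers all reported deaths and asks for relationship to study treatment. SAP 9.4 narrows the set by its label and asks only about causality to the disease. SAP 4.9 says substantive changes from protocol analyses are documented. It names the addition of PFS2 and nothing about deaths.

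**Step 4: an illustration of size, on assumed inputs.** Let O be the time from last dose to onset of the fatal event, exponential, and let D be O plus an exponential lag with mean L. The cabozantinib window of 30 days is used, with follow-up to F. The excluded share of later deaths is 1 − P(O ≤ 30, 30 < D ≤ F) / P(30 < D ≤ F). The assumed values are median survival after last dose of 3, 6, 12 or 22 months, L of 7, 14, 30 or 60 days, and F of 180 days, 365 days or unlimited. That makes 4 × 4 × 3 = 48 combinations.

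The simulated share runs from 0.643 (3 months, 60 days, 180 days) to 0.993 (22 months, 7 days, unlimited).

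A closed form checks one unlimited case, 3 months and 60 days:
- Mean time to death is 3 × 30.4375 / ln 2 = 131.7 days, so mean onset is m = 131.7 − 60 = 71.7 days.
- P(O > 30) = exp(−30/71.7) = 0.658.
- P(O ≤ 30, D > 30) = [60/(71.7 − 60)] × (0.6582 − 0.6065) = 0.264.
- Excluded share = 0.658 / (0.658 + 0.264) = 0.713, against 0.714 simulated.

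The model places every fatal onset after last dose. Events that began on treatment and proved fatal after day 30 are left out, which pushes the share up. None of these inputs comes from the documents.

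**The case against.** The strongest reply is that the parenthetical is only a loose label. SAP 9.4 speaks of all deaths, orders a row for deaths after 30 days, and promises a listing of all reported deaths. The TEAE definition has no upper time limit. SAP 4.6 allows exceptions specified in the plan, and an explicit later row can be read as one. Protocol 9.6.1 still stands, with no departure recorded.

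This is probably the intent, and under it both the shortfall and the difference between arms disappear. But the SAP does not say so. Where SAP 9.1 wants an exception to the observation period, it marks one: the adverse event overview counts treatment-related deaths without a time limit. No such marking is attached to the death table, and its data source is not named.

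The reply is right about consequence. All deaths are listed. OS counts deaths from any cause up to cutoff in the OITT and ITT populations. Related Grade 5 TEAEs are summarized in SAP 9.1, so relationship to treatment is partly covered.

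**Conclusion.** The conflict is real but narrow. Taken literally, SAP 9.4 restricts its later row to deaths from events that began inside the observation period, makes the within-30-day row unequal between arms, and falls short of Protocol 9.6.1. The effect is confined to one descriptive table and its O-Safety counterpart. No primary or OS result changes.

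A reader might infer that the trial would lose deaths or misstate mortality by arm. The documents do not support that, given the listing and the OS analysis. A reader might also look for a count or percentage of deaths lost. The documents give none, and the illustrative range rests wholly on assumed survival times and lags. The share of all deaths that occur late would be a different quantity again, since it does not say how many of them the rule excludes. Nor should the corrected table be expected to match the OS event count: it uses the Safety populations, with SAP 3.3 grouping by treatment actually received, whereas OS uses the OITT and ITT populations.

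**What to change.** In SAP 9.4, delete the parenthetical that equates deaths with Grade 5 TEAEs. State that the table uses all reported deaths up to data cutoff in the Safety and O-Safety populations, drawn from AE/SAE and survival follow-up records, regardless of the safety observation period. This also removes the difference between arms in this table without altering SAP 4.6.

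Group by actual treatment received, following SAP 3.3, and show placebo-crossover subjects separately as in Table 4. Report timing category and cause of death. Report relationship to study treatment where it was collected. For deaths known only from survival follow-up, Protocol 5.4.2 lists date and primary cause but no relationship, so the table should show relationship as not collected for them. Keep Grade 5 TEAEs in the SAP 9.1 adverse event tables.

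The cost is a short SAP wording change and a combined data source for one table and its O-Safety version. No new data collection is needed.
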